#### **4.5 Patient Screening and Informed Consent**

A member of the circle of care will screen patients for broad eligibility and approach them to see if they are interested in participating in a research study. If they agree, research personnel will

confirm their eligibility. After an initial screening process following local research ethic board guidelines, eligible patients will engage in the informed consent process. To obtain informed consent, personnel at each cluster will adhere to the following procedures:

1. Present trial information in a manner that is understandable to the patient.
2. Discuss the trial with the patient and answer any questions they have.
3. Confirm that the patient understands the risks and benefits of participating in the trial and that their participation is voluntary.
4. Complete the consent process and obtain signatures from the patient and person obtaining consent.

Site research personnel will follow the process of obtaining and documenting informed consent forms in accordance with Good Clinical Practice. Participants may withdraw their consent at any time.

If a potentially ineligible participant is enrolled, at least one member of the Central Adjudication Committee will review de-identified medical records to determine eligibility. *The Central Adjudication Committee will be comprised of three members who are orthopaedic surgeons.* Their decision will be based on the information available at the time of informed consent.

#### **4.6 Intervention**

Research personnel at each cluster will inform individual participants of their treatment allocation **after** they have provided informed consent. Participants enrolled during the usual care phase at their clinic will attend appointments as usual on a schedule determined by their surgeon and will not have access to social worker support in the fracture clinic.

Participants enrolled during the treatment phase at their clinic will receive social work support (see Table 1) for 6 months from the time of enrollment. They will have an intake appointment with the social worker before or during their initial fracture clinic visit to assess their needs, identify goals that they can address with the support of the social worker, and collaboratively formulate a personalized care plan tailored to their specific circumstances. The social worker will then implement the plan, which may involve educating participants and their support network, coordinating delivery of care and benefits, making referrals to community services, advocating for the participant, and providing emotional support and brief counselling. The social worker will be accessible to participants for 6 months post-enrollment, following up via telephone, telemedicine or in-person to evaluate the effectiveness of the care plan and offer sustained ongoing support. During this time, the social worker will make detailed notes on communication and referrals provided.

Table 1: Social Worker Support

1. Intake and Assessment: The social worker will complete a standardized intake assessment questionnaire that will ask the participant about their social needs. This will include asking about safety, intimate partner violence, addictions, housing and utilities, finances, food insecurity, mental health, transportation, and injury recovery.
2. Formulation of goals: Based on the intake and assessment, the social worker will work with the participant to identify goals the social worker can help the participant achieve. An example of a goal is “plans for childcare during physiotherapy appointments”; “manage my stress and anxiety since the car accident”; “help to stop drinking”; “try to get off pain medications”; or “get a walker while on a fixed income”.
3. Treatment planning and intervention: The social worker will perform interventions according to the established goals. These can include management of patient expectations, advocacy for participant, coordination of care and benefits, referrals to community service partners, patient and family education, and emotional support and brief counselling.
4. Evaluation and Termination: The social worker will revisit the planned goals with the participant at each follow-up appointment, discuss progress, and provide additional treatments, resources, and referrals.

## 4.7 Outcomes

The primary outcome measure is all cause visits to an emergency room or urgent care centre within six months of enrollment. (See Section 4.7.1).

Secondary outcome measures are:

1. LIMB-Q Psychological Impacts scale (See Section 4.7.2).
2. LIMB-Q Financial Impacts scale (See Section 4.7.2).
3. Satisfaction with care provided (See Section 4.7.3)
4. Opioid use (See Section 4.7.4).
5. Fracture clinic visits attended and missed (See Section 4.7.5)
6. Economic analysis (EQ-5D-5L and hospital use) (See Section 4.7.6)
7. Qualitative interviews with participants, social workers, and health care professionals (See Section 4.7.7).

### 4.7.1 Number of Emergency Room and Urgent Care Center Visits

Research personnel will ask participants if they went to the emergency room or to an urgent care facility at each of the follow-up visits 6 weeks, 3 months, and 6 months after consent. Additionally, research personnel will review the participant’s medical records for emergency room and urgent care visits. We will document the date of any visits and the reason for the visit. We will also document whether the visit occurred at the same or different hospital and hospital system where the participant is receiving care for the fracture.

#### *4.7.2 LIMB-Q*

The LIMB-Q is a validated questionnaire with 16 independently functioning scales designed specifically for patients with extremity injuries. This trial will use the LIMB-Q Psychological and Financial impact scales as secondary outcome measures. Research coordinators will administer all LIMB-Q scales at baseline, 6 weeks, 3 months, and 6 months after consent. LIMB-Q scale scores range from 0 (worst) to 100 (best). Higher scores for LIMB-Q scales reflect a better outcome. To provide a point of reference for the LIMB-Q, we will also administer the EQ-5D. This is a standardized instrument for use as a measure of health status that has been validated in similar patient populations. It uses a descriptive system composed of 5 dimensions of health (mobility, self-care, usual activities, pain/discomfort, and anxiety/depression). Each dimension is comprised of five levels: no problems, slight problems, moderate problems, severe problems and extreme problems. A unique EQ-5D health state is defined by combining 1 level from each of the 5 dimensions. It is also a cognitively simple test, taking only a few minutes to complete but with the capacity of collecting health utility data. Research coordinators will administer the EQ-5D at baseline, 6 weeks, 3 months and 6 months after consent.

#### *4.7.3 Satisfaction with Care Provided*

At each follow-up, participants will be asked a single, Likert-scale question about their level of satisfaction with the care they have received for their fracture(s).

#### *4.7.4 Opioid Use*

We will assess the use of opioid medications at baseline, 6 weeks, 3 months and 6 months post-consent.

#### *4.7.5 Missed Fracture Clinic Visits*

We will assess the proportion of missed clinic visits by tracking the number of fracture clinic visits each participant attends as well as tracking any missed clinic visits. We will ask the participant about appointment attendance as well as verify information from their medical record.

#### *4.7.6 Economic Analysis*

We will conduct a cost-effectiveness analysis from the payer's perspective which will include utilities obtained from the Euro-Quol-5 Dimensions 5 Levels (EQ-5D-5L), the cost of the social worker, and the hospital care costs. The EQ-5D is a widely-used, standardized instrument for measuring health-related quality of life, which has been validated for the proposed patient population. The EQ-5D-5L allows the calculation of a health utility score, which is necessary to calculate quality-adjusted life years (QALYs). QALYs combine quantity of life with Health-Related Quality of Life and are used in cost-effectiveness analyses to compare outcomes between interventions. We will calculate QALYs for each intervention by weighing the utility scores by time spent in health states using an area under the curve approach. Participants will be asked to record hospital visits and research personnel will verify this information in their medical record. This data will be modeled within the economic analysis to compare the social worker intervention versus usual care.

#### *4.7.7 Lived Experiences of Orthopaedic Trauma Patients, Social Workers, and Health Care Professionals in Fracture Clinics*

We will conduct qualitative interviews in alignment with the CORE-Q guidelines for qualitative research. We have selected qualitative description as the theoretical basis the qualitative component of this trial. Qualitative description is a low-interpretation method of analyzing qualitative interviews that does not describe themes in terms of a conceptual, philosophical or other highly abstract framework or system^16. We will also use this approach for the social worker and health care professional interviews.

We will conduct one-on-one interviews with 25-30 participants who have completed the trial. The interviews will be structured, with approximately 20 questions expected to allow for 30-45 minutes interview length. Interviews will take place over Zoom, telephone, or in-person, depending on the preference of the participant. The interviews will be audio-recorded for transcription. Sampling for the interviews will be split equally between participants from the intervention and usual care groups and will follow a maximum variation technique, in order to provide information from a broad range of perspectives.

Separately, we will conduct interviews with each of the social workers and 10-12 interviews with health care professionals in the fracture clinics. These interviews will follow the same process as the participant interviews. We will follow an informed consent procedure with social workers and health care professionals who participate in qualitative interviews to address the exploratory objective.

### **4.8 Data Collection and Participant Follow-Up**

#### *4.8.1 Data Collection Procedures*

After obtaining informed consent from a participant, research personnel will complete the baseline case report forms (CRFs). Baseline data will be obtained from the participant, the participant's medical record, and/or the participant's treating physicians and entered by the Research Coordinator. Baseline data collection points include participant and injury characteristics such as age, sex, gender, socioeconomic status, co-morbidities, mechanism of injury, among others. At baseline, participants will also complete the LIMB-Q scales, the satisfaction with care question, opioid use question, and the EQ-5D.

#### *4.8.2 Participant Follow-Up*

We will follow participants for 6 months after enrollment, as this aligns with the usual clinical follow-up timeline for orthopaedic injuries. Table 1 below indicates the timeline for baseline and follow-up completion of CRFs. Follow-up may be completed in-person at the fracture clinic, by telephone, by mail, or via secure electronic methods. Research personnel may also review the participant's medical records for emergency room and urgent care visits.

The social worker at each clinic will document the social work interactions by maintaining a log that documents each point of contact they have with each participant. This log will include the

medium of contact, themes discussed, and number of referrals made. At each trial follow-up visit, we will ask participants if they saw a social worker outside of the fracture clinic and document any care referrals that they received.

Table 1: Follow-up Schedule				
	Enrollment and Baseline	6 Weeks (Day 42) (22 to 62 days post-enrollment)	3 Months (Day 90) (63 to 117 days post-enrollment)	6 Months (Day 180) (118 to 242 days post-enrollment)
Demographics and comorbidities	X			
Injury and treatment details	X			
Social worker interactions and referrals		Ongoing		
Emergency room and urgent care visits		X	X	X
LIMB-Q Psychological Impacts Scale	X	X	X	X
LIMB-Q Financial Impacts Scale	X	X	X	X
Satisfaction with care question	X	X	X	X
Opioid use	X	X	X	X
Fracture clinic visit attendance	X	X	X	X
EQ-5D questionnaire	X	X	X	X
Hospital use questions	X	X	X	X

#### 4.9 Blinding

Due to the nature of the intervention, it will not be possible to blind participants, trial personnel, or clinicians to treatment allocation. Data analysts and investigators responsible for interpreting results will be blinded to treatment allocation until all data have been analyzed and interpreted.

#### 5.0 SAMPLE SIZE

We chose our sample size to detect differences between the social worker intervention and usual care groups for all-cause visits to emergency room or urgent care centers (primary outcome). We estimated our sample size in accordance with the methodology of Kasza et al. using the R swdpwr package. For a binary outcome, the required cluster period size in a batched stepped wedge cluster randomized trial for a desired level of power depends on the number of time periods, number of clusters assigned to each sequence, number of sequences, number of batches, number of periods of overlap between successive batches, effect size, and ICC parameters. We will assume

80% study power with a two-sided Type I error rate of 5%, either two, three, or four batches of four sequences over five time periods, one cluster allocated to each sequence, no period overlaps, a 10% prevalence rate in the treatment group, a 14.8% prevalence rate in the control group, and a within-period intra-cluster correlation coefficient of 0.05. Based on these assumptions, we will require a total sample size of 1880 patients (cluster size of 47 patients per period) for two batches, 1800 patients (cluster size of 30 patients per period) for three batches, and 1760 patients (cluster size of 22 patients per period) for four batches. (**Table 2**). To account for a 10% loss to follow-up rate, the total sample size, regardless of the batch size, will be rounded to 2000.

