**Table 2: Sample Size Calculations**

		Prevalence of Outcome in Treatment Group		
		8%	10%	12%
		Two Batches		
Intracluster Correlation Coefficient (ICC)	0.005	760	1680	5560
	0.01	800	1760	5680
	0.05	880	1880	5840
	0.1	920	1920	5880
	Three Batches			
	0.005	720	1620	5400
	0.01	780	1680	5580
	0.05	840	1800	5700
	0.1	900	1860	5760
	Four Batches			
	0.005	720	1600	5360
	0.01	720	1680	5520
	0.05	800	1760	5680
	0.1	880	1760	5520

*Note:  $\alpha = 0.05$ , power = 80%, sampling structure = cross-sectional sample, sequences = 4, periods=5, number of periods of overlap between successive batches = 0, prevalence of outcome in control group = 14.8%*

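### The stated sample sizes give 80% power only if period effects are ignored; with period in the model, power for 14.8% versus 10% is about 43–44%

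*Protocol*

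**What the plan says.** Section 5.0 sizes the trial on a binary outcome, any emergency room or urgent care visit, at 80% power and two-sided 5%. The design inputs are "either two, three, or four batches of four sequences over five time periods" and "one cluster allocated to each sequence, no period overlaps". The rates are "a 10% prevalence rate in the treatment group, a 14.8% prevalence rate in the control group", with "a within-period intra-cluster correlation coefficient of 0.05". The result is that "we will require a total sample size of 1880 patients (cluster size of 47 patients per period) for two batches"; three batches need 1800 (30 per cluster-period) and four need 1760 (22 per cluster-period). The total is then set at 2000 for 10% loss to follow-up.

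The note to Table 2 repeats the structure: "sampling structure = cross-sectional sample, sequences = 4, periods=5, number of periods of overlap between successive batches = 0". Section 5.0 says that the required size depends on ICC parameters in the plural, but gives a value only for the within-period one. Neither the text nor the note mentions a period or secular-trend effect. The outline of the primary model in Section 6.1 lists treatment, cluster and prognostic covariates, with no term for period.

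**The concern.** Section 3.1 has every clinic in a batch start in usual care, cross over one at a time at 10, 20, 30 and 40 weeks, and finish under the intervention. The treated share of the four clinics is therefore 0, 1/4, 1/2, 3/4 and 1 across the five periods. Any drift in emergency or urgent care use over the year runs in parallel with the rollout. An estimate without period terms credits that drift to the social worker. Period adjustment removes the bias, but it also removes much of the information on treatment.

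The stated totals are only about 1.3 times the size needed under individual randomisation, which is too small an inflation for a period-adjusted stepped wedge. If the 80% was computed without period effects, a properly adjusted analysis would more likely than not miss the effect the trial is sized for, and a null result could be misread as evidence of no benefit. Section 6.5 plans no interim analysis, so nothing during the trial would reveal the shortfall.

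**Working it through.** **Inputs (Section 5.0 and Table 2 note).** Control rate 0.148, treatment rate 0.10, difference δ = 0.048. Two-sided α = 0.05. B = 2, 3 or 4 batches, 4 sequences × 5 periods, one cluster per sequence, n = 47, 30 or 22 per cluster-period, within-period ICC ρ = 0.05, cross-sectional sampling. The between-period ICC ρ₁ is not stated; it is taken as 0.05 (the favourable case), and lower values are shown as a range.

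**Formula.** Generalised least squares on cluster-period means. The covariance matrix V of a cluster has diagonal p(1−p)[ρ + (1−ρ)/n] and off-diagonal √(v_j v_k)·ρ₁, where v = p(1−p) in each cell. Var(δ̂) is the treatment element of (B·Σ Z′V⁻¹Z)⁻¹, summed over the four sequences. Z holds treatment plus either one intercept (no period effects) or five period indicators. Power = Φ(δ/SE − 1.96).

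**Step 1: the plan's own figure, no period effects.**

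| Batches (n) | SE | δ/SE | Power at stated N | N for 80% | Stated N |
|---|---|---|---|---|---|
| 2 (47) | 0.01693 | 2.835 | 80.9% | 46 × 40 = 1840 | 1880 |
| 3 (30) | 0.01702 | 2.820 | 80.5% | 30 × 60 = 1800 | 1800 |
| 4 (22) | 0.01704 | 2.817 | 80.4% | 22 × 80 = 1760 | 1760 |

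Across the 36 cells of Table 2, this calculation is exact in 22. Thirteen of the other 14 differ by one patient per cluster-period and one differs by two.

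**Step 2: the same calculation with categorical periods.**

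| Batches (n) | SE | δ/SE | Power at stated N | N for 80% |
|---|---|---|---|---|
| 2 (47) | 0.02660 | 1.804 | 43.8% | 122 × 40 = 4880 |
| 3 (30) | 0.02674 | 1.795 | 43.4% | 79 × 60 = 4740 |
| 4 (22) | 0.02670 | 1.798 | 43.6% | 58 × 80 = 4640 |

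Periods shared across batches or specific to each batch give the same result. The variance rises by a factor of about 2.47 (for two batches, (0.02660/0.01693)² = 2.47). Over all Table 2 cells the period-adjusted N is 2.2 to 2.7 times the printed one.

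**Step 3: a check by hand.** Individual randomisation needs N = 2(1.960 + 0.842)²[0.148 × 0.852 + 0.10 × 0.90]/0.048² = 1472. Under 1:1 randomisation the treatment indicator has variance 0.25. In this design the sequences are treated for 4/5, 3/5, 2/5 and 1/5 of the time, so the mean within-cluster variance is (0.16 + 0.24 + 0.24 + 0.16)/4 = 0.20. The inflation is 0.25/0.20 = 1.25, and 1.25 × 1472 = 1840. Removing period as well takes out the variance of the treated share (0, 0.25, 0.5, 0.75, 1), which is 0.125. That leaves 0.075; the inflation is 0.25/0.075 = 3.33, and 3.33 × 1472 is about 4900. The stated 1880/1472 = 1.28 fits the first case, not the second.

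**Step 4: sensitivity at the stated N, period-adjusted (two / three / four batches).**
- Logit link: 43.2% / 42.9% / 43.0%. Log link: 42.5% / 42.3% / 42.6%.
- One linear trend in place of categorical periods: 44.2% / 43.8% / 43.9%.
- Other ICCs in Table 2, with ρ₁ = ρ: 51–52% at 0.005, 48–49% at 0.01, 43–44% at 0.1.
- ρ₁ below ρ = 0.05 (assumed values): 33% / 36% / 38% at ρ₁ = 0.04; 25% / 30% / 33% at ρ₁ = 0.025.
- All 2000 evaluable: 45.9% / 47.0% / 47.8%.

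Even without period effects, a lower between-period ICC breaks the claim: 66–73% at ρ₁ = 0.04 and 51–64% at 0.025.

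**Step 5: what 2000 buys.** 2000 × 0.9 = 1800 evaluable, or 45 / 30 / 22.5 per cluster-period. Period-adjusted power for 14.8% versus 10% is 42.4% / 43.4% / 44.3%. Power of 80% is reached at a treatment rate of about 7.4% / 7.6% / 7.7%.

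**The case against.** The protocol never says that period effects were set to zero; this is inferred from how closely the table reproduces, and the match is not perfect (the two-batch figure is one patient per cluster-period off). That is fair as a caution about the cause. It does not help the figure: under every link and form of trend tried, the period-adjusted calculation stays far below 80% at the stated N.

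Power belongs to a design together with its analysis, and Section 6.1 outlines a model without period terms. For that analysis, 80% is internally consistent. This also stands, but it makes the claim conditional on there being no secular trend at all, an assumption Section 5.0 does not state and the design cannot guarantee.

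The size of the loss depends on the ICC: at 0.005 power is slightly above one half. So 43–44% belongs to the protocol's chosen ICC of 0.05, not to every row of Table 2. No row comes near 80%.

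Period terms could be left to the SAP. The model details could be, but the sample size and its power are fixed in the protocol, and adding period terms in the SAP is what would bring the 44% into effect.

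Finally, Section 6.1 names a Cox model, whereas Section 5.0 sizes a binary outcome. The check follows the protocol's own binary basis.

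**Conclusion.** The concern holds. The stated 1880 / 1800 / 1760 correspond to 80% power only with no period effects and with the between-period ICC equal to the within-period ICC. With period effects and an ICC of 0.05 constant over periods, power for 14.8% versus 10% is 43.8% / 43.4% / 43.6%, and 80% power needs 4880 / 4740 / 4640 evaluable patients, about 2.6 times the stated numbers. The calculation rests on a Wald test, arm-specific binomial variances, equal cluster-period sizes and the design inputs of Section 5.0. Equal ICCs is the favourable case; a decaying correlation lowers power further. This needs correcting before the power claim can stand.

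**What to change.** Recompute Section 5.0 and Table 2 with categorical period effects, and state the between-period ICC explicitly, for example over a range of 0.8 to 1.0 times the within-period value. Name the period structure in the Table 2 note so that the calculation can be reproduced, and bring the outline of the primary model in Section 6.1 into line with it.

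Then restate what 2000 enrolled (1800 evaluable) deliver with a constant ICC of 0.05: about 43% power for 14.8% versus 10%, or 80% power for 14.8% versus about 7.5%.

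The correction itself costs a rerun of the sample-size program and an amended section with a less favourable power figure; it requires no extra enrolment. It does leave the sponsor a decision. Keeping 80% power for a 10% treatment rate would take 4640 to 4880 evaluable patients, or about 5160 to 5420 enrolled after dividing by 0.9 for loss. The alternatives are to justify a larger target effect, change the design, or accept the lower power openly.

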## 3.0 TRIAL DESIGN

### 3.1 Description of the Trial Design

[figure not shown]
To efficiently and effectively address the above objectives, we have designed this trial as a batched stepped-wedge cluster randomized trial. The batched stepped-wedge cluster randomized trial is a pragmatic design commonly used in the evaluation of service delivery interventions. In the batched stepped wedge trial, clusters (in this case, surgeon clinics) of patients can be randomized and move through the trial design in ‘batches’ (e.g. a group of four clusters), which allows for flexibility in the timing of initiation of different clusters. The stepped wedge design itself begins with each cluster in the batch being given a date for crossover into the treatment group, in a randomly determined order. All clusters then enter an initial period in which no patients are exposed to the intervention. Subsequently, at regular intervals (“steps”), clusters cross from the control to the intervention under evaluation. This process continues until all clusters have crossed over to the intervention. At the end of the batch period there is a period when the intervention is being

implemented at all clusters. Data collection takes place throughout the batch period, so that all clusters contribute observations under both control and intervention observation periods. We will define a cluster as an individual orthopaedic surgeon fracture clinic.

We will conduct this trial in two to four batches, with four clusters in each batch. The number of batches will depend on the enrollment rates during the previous batches. For each batch, before participant enrollment begins, the Methods Centre will randomize the clusters (i.e. clinics) to determine when they will begin the intervention (i.e. social worker support in the fracture clinic). All clinics in the batch will begin participant enrollment into the non-intervention arm (i.e. usual care with no social worker services). At 10 weeks, one clinic will begin the intervention while the others will continue enrolling in the non-intervention arm as per randomization. At 20 weeks the second clinic will cross over to begin treatment, and at 30 weeks the third clinic will crossover. The fourth clinic will cross over after 40 weeks. All clinics (clusters) will enroll for 12 months.

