To ensure feasibility of this design, we will conduct a Vanguard phase that will include two clusters who will enroll for a period of 8 months. As per the above, both clusters will be participant enrollment into the non-intervention arm (i.e. usual care with no social worker services). At 10 weeks, one cluster will begin the intervention while the other cluster will continue enrolling in the non-intervention arm as per randomization. At 20 weeks the second cluster will cross over to begin treatment. Participant enrollment in both clusters will continue for 10 additional weeks. Data from the vanguard phase will be included in the trial, if there are no significant changes to the protocol.

Figure one shows the trial design, which includes the vanguard phase (in purple) and then a batched stepped-wedge design (in green). Batch timelines may also overlap each other, and the timing will depend upon funding and the readiness of different clusters to begin recruitment. The overall sample size for the trial will be approximately 2,000 participants.

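### The total of 2000 does not allow for 10% loss to follow-up when only two batches are run: it allows for 6%

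*Protocol*

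**What the plan says.** Section 5.0 and Table 2 give the number of patients needed at an intracluster correlation of 0.05, with event rates of 14.8% under control and 10% under treatment, 80% power and a two-sided 5% test. For the smallest design the figure is "1880 patients (cluster size of 47 patients per period) for two batches". The corresponding totals are 1800 (30 per period) for three batches and 1760 (22 per period) for four. These figures precede any allowance for loss. The allowance follows in one sentence: "To account for a 10% loss to follow-up rate, the total sample size, regardless of the batch size, will be rounded to 2000".

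Section 3.1 leaves the number of batches open: "We will conduct this trial in two to four batches, with four clusters in each batch". The choice is made during the trial: "The number of batches will depend on the enrollment rates during the previous batches". On the total, Section 3.1 says "The overall sample size for the trial will be approximately 2,000 participants", and the Trial Summary gives 2000 patients. The two vanguard clusters enter only conditionally: "Data from the vanguard phase will be included in the trial, if there are no significant changes to the protocol".

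**The concern.** A single total is claimed to absorb 10% loss whichever number of batches is used, yet the three requirements differ by 120 patients between the smallest and largest design. One inflated figure can cover all three only if it is large enough for the most demanding, which is two batches. If 2000 falls short there, the protocol misstates its loss allowance for a design it may adopt. Anyone deciding whether to stop at two batches would rely on this sentence.

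**Working it through.** **Inputs.** Required totals, cluster-period sizes, event rates, intracluster correlation, 10% loss and the final 2000 all come from Section 5.0. Each batch has four clusters and five periods, so two, three and four batches give 40, 60 and 80 cluster-periods.

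**The plan's own totals before loss.** Cluster-periods × size: 40 × 47 = 1880; 60 × 30 = 1800; 80 × 22 = 1760. All three agree with the text and with Table 2.

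**Inflation for loss.** Enrolled number = N / (1 − 0.10). Loss covered by 2000 = 1 − N/2000.

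| Batches | N required | N / 0.9, rounded up | Loss covered by 2000 | Left per cluster-period after 10% loss | Required per cluster-period |
|---|---|---|---|---|---|
| Two | 1880 | 2089 | 6.0% | 1800/40 = 45 | 47 |
| Three | 1800 | 2000 | 10.0% | 1800/60 = 30 | 30 |
| Four | 1760 | 1956 | 12.0% | 1800/80 = 22.5 | 22 |

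The stated 2000 is exact for three batches and sufficient for four. For two batches it is 2089 − 2000 = 89 short (4.3% of 2089), which leaves 1880 − 1800 = 80 too few evaluable patients. The cruder rule N × 1.1 gives 2068 for two batches, also above 2000.

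**Effect on power.** The protocol does not state its power model, so this part is a reconstruction. It uses generalised least squares on cluster-period means, a cross-sectional sample, an exchangeable correlation of 0.05 within and between periods, binomial variances, no period effects, no vanguard clusters and a two-sided 5% test.

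| Evaluable per cluster-period, two batches | Identity link | Logit link |
|---|---|---|
| 47 (as required) | 80.9% | 80.3% |
| 46 | 80.2% | 79.5% |
| 45 (2000 enrolled, 10% lost) | 79.4% | 78.7% |

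The smallest size reaching 80% is 46 with the identity link (total 1840) and 47 with the logit link (total 1880, the protocol's figure). The identity-link version returns 1800 and 1760 for three and four batches.

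**With the vanguard clusters inside the 2000.** Two clusters over three periods add 6 cluster-periods, 46 in all. After 10% loss, 1800/46 = 39.1 per cluster-period, and power is 80.5% (identity) or 79.8% (logit).

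**The case against.** The case for leaving the sentence alone has several parts.

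- **It is a rounded planning target.** Section 3.1 says the total is approximate, and one recruitment target is convenient while the number of batches is undecided. That explains the choice of 2000. It does not make 2000 a 10% allowance for two batches, since both 2089 and 2068 would have to be rounded down.
- **The vanguard clusters make up the difference.** They largely do, as the last calculation shows. But their inclusion is conditional, and Section 5.0 takes no credit for them, so they cannot support an unconditional claim made there.
- **A lost participant may still contribute.** Visits are also sought in medical records (Section 4.7.1), and the primary analysis is a Cox model (Section 6.1), so follow-up time before loss can count. This may soften the real shortfall. Section 5.0, however, sizes the trial on a binary outcome and chose to inflate for loss on that basis, so the inflation should be right on that basis.
- **The power figures depend on an assumed model.** This stands. With the identity link, 2000 holds 80% power up to 8% loss (1 − 1840/2000). With categorical period effects fitted, two-batch power at the same inputs is about 44% at 47 per cluster-period and 42% at 45. The power levels above therefore hold only without period effects. The loss coverage of 6%, 10% and 12% needs no power model.

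**Conclusion.** The concern holds. The claim in Section 5.0 is right for three and four batches and wrong for two, where 2000 covers 6% loss and 10% loss leaves 80 fewer evaluable patients than required. This follows from the protocol's own figures by division. The loss of about 1.5 percentage points of power is marginal. It assumes the reconstruction without period effects, no vanguard contribution, and that a lost participant supplies no outcome. The point is a wrong stated allowance for the trial's central number. It does not threaten the design and is worth correcting because the correction is nearly free.

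**What to change.** Remove the clause in Section 5.0 that makes the total independent of the number of batches, and keep 2000 with wording such as: *With three or four batches, 2000 participants allow for at least 10% loss to follow-up. With two batches they allow for 6%; a 10% loss would leave 1800 evaluable participants and power marginally below 80%, before any contribution from the vanguard clusters.* The sponsor should check the power clause against its own software run at 45 per cluster-period. This changes one sentence, adds no patients, and leaves the 2000 in the Trial Summary and Section 3.1 as it is.

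The alternative is to state a loss-adjusted total for each option by one rule, N/0.9 rounded up: 2089, 2000 and 1956. This enrolls 89 more if two batches are used, would lower the four-batch target by 44, and means revising the Trial Summary and Section 3.1. These totals are not all whole numbers per cluster-period; rounding up within each cluster-period gives 53 × 40 = 2120, 34 × 60 = 2040 and 25 × 80 = 2000. The first option is enough.
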